## 10.1 Extent of Exposure

The summary statistics will be produced in accordance with section 8.

## 10.2 Adverse Events

For the calculation of incidence of adverse events (i.e., on a per subject basis), each subject will only be counted once and any repetitions of adverse events within a subject will be ignored; the denominator will be the number of subjects in the Treated population. All adverse events reported will be included in the summaries and analyses. Adverse events incidences will be reported by System Organ Class and Preferred Term.

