3.7. Table of endpoints/outcomes

Objectives	Outcome Measures	Timepoint(s)
Primary Objective Participant clinical status (on a 7- point ordinal scale) In accordance with WHO recommendations the primary endpoint will be determined by a pilot trial of the first 100 participants.	 7-point ordinal scale: Not hospitalised, no limitations on activities Not hospitalised, limitation on activities; Hospitalised, not requiring supplemental oxygen; Hospitalised, requiring supplemental oxygen; Hospitalised, on non-invasive ventilation or high flow oxygen devices; Hospitalised, on invasive mechanical ventilation or ECMO (Extracorporeal membrane oxygenation) Death. 	Up to day 29
Secondary Objectives	Outcome Measures	Timepoint(s)
Evaluate the clinical efficacy of Brensocatib relative to standard care in adult patients hospitalised with COVID-19	Clinical Severity Time to an improvement of one category from admission using 7-point ordinal scale. Participant clinical status on 7-point ordinal scale Mean change in the 7-point ordinal scale	Daily whilst hospitalised Days 3, 5, 8, 11, 15 and 29. Baseline to days 3, 5, 8, 11, 15 and 29.
	National Early Warning Score (NEWS): Time to discharge or to a NEWS of ≤ 2 and maintained for 24 hours, whichever occurs first. Change from baseline Oxygenation:	Daily whilst hospitalised Days 8, 15, 29
	Oxygen free days Incidence and duration of new oxygen use during the trial	1-29 days 0-29 days
	Mechanical Ventilation: Ventilator free days	1-29 days

	Incidence and duration of new mechanical ventilation use during the trial.	1-29 days
	Hospitalisation:	
	Duration of hospitalisation (days).	Date of admission and discharge
	Mortality:	
	28-day mortality	Date of death
Evaluate the safety of the	Cumulative incidence of SAEs	1-29 days
intervention through 28 days of follow-up as compared to the control arm	Discontinuation or temporary suspension of treatment	1-29 days
	Changes in white cell count, haemoglobin, platelets, creatinine, total bilirubin, ALT, and AST over time (hospitalised participants only)	Days 0/1, 3, 5, 8, 11, 15, 29
	Adverse events of special interest- hyperkeratosis, infections and dental complications	1-29 days
	dental complications	
Exploratory Objectives	Outcome Measures	Timepoint(s)
Exploratory Objectives Evaluate the virologic efficacy of Brensocatib	·	Timepoint(s) Day 15 and day 29

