8.7. Dosage schedules

Route of administration: oral. Where a participant is unable to take oral medication they will be excluded from the trial. If during the treatment phase a participant becomes unable to take oral medication their treatment will be given by nasogastric tube (NGT) where the participant has this in place for clinical reasons. After crushing, the tablet should be placed in water for 5-10 mins, after pushing through NGT, flush with 10 mL of water (or saline), and clamp NGT for 30 mins.

Frequency of administration: once daily, before breakfast. On day of randomisation the first dose may be given up to 5pm, after that point the first dose should be given the following day before breakfast. The day of first dose received will be deemed to be day 1 of the trial.

Missed doses: if a dose is missed this should be given within 10 hours of the missed dose.

Maximum duration of treatment: 28 days. Where a participant misses a dose due to being unable to take oral medication, or for any other reason, the treatment duration will not be extended.

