9.3. Recording and reporting of SAEs, SARs AND SUSARs

AEs will be recorded on the AE Log in the eCRF and will be assessed for severity and causality by the CI or PI. AEs occurring from the time a participant consents to join the trial until the participant's day 29 will be recorded. An AE may be classified as a SAE or AR. An initial assessment of expectedness/listedness for SAEs will be conducted by the PI based on the Reference Safety Information (RSI).

Participants discharged from hospital before the end of trial will be given a diary to record adverse events, this will be used as an aide memoire for them to report AEs at the telephone follow-up call. This diary will not be returned to the trial staff.

The PI will make a clinical judgment as to whether or not an AE is of sufficient severity to require the participant's discontinuation of treatment. A participant may also voluntarily discontinue treatment due to what he or she perceives as an intolerable AE. If either of these occurs, the participant should be given appropriate care under medical supervision until symptoms cease, or the condition becomes stable.

AEs and SAEs will be followed up until recovered/recovered with sequelae/death or for 30 days after participant's day 29 whichever happens first. SUSARS will be followed until resolution.

The CI, PI or delegate will check the medical records for the occurrence of AEs and hospitalisations at every data collection point/telephone call during the trial. Serious AEs (SAEs) will be submitted on an SAE form to the Sponsor Pharmacovigilance Section [contact] within 24 hours

of becoming aware of the SAE. All SAEs need to be assessed and signed off by the PI or a delegated doctor within the 24hr reporting window. Site PIs will also notify the CI when submitting an SAE.

The evaluation of expectedness will be made based on the knowledge of the reaction and the relevant safety information (RSI) in the Brensocatib Investigators Brochure (IB) (see section 9.4). The Sponsor will make the definitive assessment on expectedness for the purposes of SUSAR reporting.

The Sponsor is responsible for reporting SUSARs to the UK competent authority, the MHRA, and the Research Ethics Committee (REC). Fatal or life threatening SUSARs will be reported within 7 days and non-fatal and non-life threatening SUSARs within 15 days.

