## Safety of the intervention:

- 1. Cumulative incidence of serious adverse events (SAEs) from day 1 to 29.
- 2. Discontinuation or temporary suspension of treatment from days 1 to 28.

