#### 7.2.4 Safety Population

Safety analyses will be based a modified intent-to-treat population consisting of all participants who were randomised and received at least one dose of randomised therapy.

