## 10 Safety Analyses

Safety endpoints include cumulative incidence of SAEs, discontinuation or temporary suspension of treatment, changes in white cell count, haemoglobin, platelets, creatinine, total bilirubin, ALT and AST over time. Adverse events of special interest; hyperkeratosis (skin), infection, and dental complications will be reported. These events will be analysed univariately. The proportion of participants who had adverse events will compared between both the groups using Poisson regression. Adverse events leading to premature discontinuation from the study intervention and serious AEs will be presented either in a table or a listing.

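### The any-AE and SOC/PT comparisons have no first-dose cut-off, so adverse events between consent and dosing count and pull a true risk ratio slightly towards 1

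*SAP*

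**What the plan says.** **Collection.** Protocol 9.3 provides that "AEs occurring from the time a participant consents to join the trial until the" participant's day 29 are to be recorded.

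**Analysis.** SAP 10.2 states "All adverse events reported will be included in the summaries and analyses". For incidence, "each subject will only be counted once and any repetitions of adverse events within a subject will be ignored", and the denominator is the Treated population. SAP 7.2 does not define that name, but the safety population in SAP 7.2.4 is "participants who were randomised and received at least one dose of randomised therapy". SAP 10 adds: "The proportion of participants who had adverse events will compared between both the groups using Poisson regression". SAP 10.2 also reports incidences by SOC and PT. Neither section defines a treatment-emergent event or sets a start date for counting.

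**Time between consent and dose.** Protocol Appendix 4 allows randomisation within 24 hours of screening. Protocol 8.7 permits a first dose on the day of randomisation until 5pm; "after that point the first dose should be given the following day before breakfast". The day of first dose is day 1.

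**Other windows.** SAP 4.2 defines the serious-event endpoint as "Cumulative incidence of serious adverse events (SAEs) from day 1 to 29". Protocol 3.7 lists "Cumulative incidence of SAEs" and the events of special interest (hyperkeratosis, infections, dental complications) at 1 to 29 days. The schedules in Protocol Appendix 4 and SAP 5.4 start AE recording in the randomisation column. Protocol 9.1 defines an AE as occurring in someone who has been given a medicinal product.

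**The concern.** The numerator opens at consent, while the denominator is restricted to people who were dosed. Because each participant counts once, someone with an event in the hours before the first tablet is already a case, and nothing that happens on drug can change that. Such events cannot be caused by the drug and are expected equally often in both arms. They therefore add the same background to both arms and move a true ratio, in either direction, towards 1. In a safety comparison that means understating an excess. The results affected are the any-AE effect estimate (SAP Table 10 and the preliminary analysis in SAP 7.6) and the SOC and PT incidences (SAP Tables 12 and 13).

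The documents also give three starting points for AEs (consent, randomisation, day 1), so two programmers could build different tables from the same data.

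**Working it through.** The plan states no AE rate and no safety risk ratio, so there is no figure of its own to reproduce. The size below rests on assumed risks.

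**Step 1: length of the pre-dose period.** Screening to randomisation is at most 24 h. Randomisation just after 5pm to an assumed 8am breakfast is 15 h. The maximum is 24 + 15 = 39 h, or 39/24 = 1.625 days. If recording starts at randomisation, as the schedules have it, the maximum is 15 h, or 0.625 day.

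**Step 2: formulas.** Let p0 and p1 be the true risks from first dose to day 29 on placebo and active, and q the probability of a pre-dose event, the same in both arms.

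- Observed risk = q + (1 − q)p
- Observed ratio = [q + (1 − q)p1] / [q + (1 − q)p0]
- Constant daily hazard h = −ln(1 − p0)/29, and for a pre-dose period of d days q = 1 − exp(−h·d)

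**Step 3: numbers.** For p0 = 0.30, h = 0.3567/29 = 0.0123 per day. At d = 1.625, q = 0.0198, the observed risks are 0.4119 and 0.3139, and their ratio is 1.312.

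| True risks (active vs placebo) | True ratio | d = 0.5 | d = 1 | d = 1.625 |
|---|---|---|---|---|
| 40% vs 30% | 1.333 | 1.327 | 1.320 | 1.312 |
| 20% vs 10% | 2.00 | 1.982 | 1.965 | 1.944 |
| 22.5% vs 30% | 0.75 | 0.755 | 0.760 | 0.766 |
| 30% vs 30% | 1.00 | 1.00 | 1.00 | 1.00 |

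Starting at randomisation (d = 0.625), 40% vs 30% gives q = 0.0077 and 0.4046/0.3054 = 1.325.

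**Step 4: power.** With 200 per arm (400 randomised 1:1) and two-sided 5%, power for 40% vs 30% falls from 55.5% to 54.7% (d = 0.5), 54.0% (d = 1) or 53.2% (d = 1.625).

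**Step 5: sensitivity to q.** If the pre-dose hazard is three times the later one, 1.333 becomes 1.314, 1.296 and 1.276 for the same three periods, and 2.00 becomes 1.948, 1.901 and 1.848. Setting q directly for 40% vs 30%, 1% gives 1.322, 2% gives 1.312, 5% gives 1.284 and 10% gives 1.243.

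**Step 6: a rare event category.** Take 5% vs 2%, a true ratio of 2.50. At a constant hazard over 1.625 days, q = 0.0011 and the ratio is 0.0511/0.0211 = 2.42.

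**The case against.** The strongest reply is that the documents already limit most of this. Serious and special-interest events carry a day 1 to 29 window, and day 1 is the day of first dose, so events on earlier days fall outside those endpoints. Both schedules start AE recording at randomisation, and the AE definition presupposes that a product has been given, which makes Protocol 9.3 the outlier. Protocol 7.8 has qualifying participants randomised at once, and screening and randomisation may fall on the same day. Protocol 9.2 keeps common COVID-19 symptoms, changes in renal and liver function and blood counts, and deterioration of COVID-19 short of death out of AE recording, which lowers q. (SAP Table 13 nevertheless has rows for cough, diarrhoea, headache and pyrexia.)

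Most of that stands, and it keeps the effect small. It does not close the gap. Nothing limits the any-AE comparison or the SOC and PT tables. Day 1 is a calendar day on which the dose may come as late as 5pm, so events earlier that day still fall inside the window. SAP 10, SAP 10.2 and Table 10 do not repeat the window, so literal programming of SAP 10.2 would count everything from consent.

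A reader might go further and infer that special-interest results are badly diluted, for example that 2.50 falls to 1.74 or 1.41 when 2% or 5% of participants have a pre-dose event. The documents do not support this. It needs 2% to 5% of participants to have that same rare event within about 39 h, roughly 18 to 45 times the later placebo hazard. A pre-dose event of another kind does not make someone a hyperkeratosis or dental case.

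**Conclusion.** The point holds as a small, avoidable flaw in a stated analysis rule. For the any-AE comparison and the SOC and PT incidences, events that the drug could not have caused are counted, and in expectation a true ratio moves slightly towards 1. Under a constant hazard and a pre-dose period of half a day to about 39 h, 1.33 becomes 1.31 to 1.33 and 2.0 becomes 1.94 to 1.98, with a loss of about 1 to 2 points of power in the 40% vs 30% example. Larger shifts need pre-dose events to be much more frequent than later ones. For serious and special-interest events only day-1 events before the dose are in question.

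All sizes rest on assumed AE risks, an assumed 8am breakfast and equal pre-dose risk in the arms, which randomisation secures only on average. A null ratio stays null in expectation. The efficacy analysis and the sample size are unaffected.

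A reader might also infer that the SAP labels pre-dose events as on-treatment. It does not; it simply sets no cut-off.

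**What to change.** - In SAP 10 and 10.2, restrict the between-arm AE, SAE and special-interest comparisons, and the SOC and PT incidences, to events with onset or worsening at or after the first dose and up to day 29.
- List pre-dose events separately, so that nothing collected under Protocol 9.3 is lost.
- Count day-1 events with a missing onset time as post-dose.
- State one start point for AE recording and one for AE analysis, and reconcile Protocol 9.3 with Protocol 9.1, Protocol Appendix 4, SAP 4.2 and SAP 5.4.

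The cost is a few lines of SAP text and one filter on onset date and time against first-dose time, which can be applied without knowing allocation. The downside is small: the missing-time default leaves some day-1 pre-dose events in the comparison. Sample size and visits do not change.

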# 10.3 Deaths, Serious Adverse Events and other Significant Adverse Events

Listings of death and other serious adverse events will be presented.

## 10.4 Pregnancies

For any subjects in the Treated population who become pregnant during the study, every attempt will be made to follow these subjects to completion of pregnancy to document the outcome, including information regarding any complications with pregnancy and/or delivery.

## 10.5 Clinical Laboratory Evaluations

Clinical safety laboratory adverse events are collected Day 0/1, 3, 5, 8, 11 and Day 15 and 29 if able to return to clinic or still hospitalized. Parameters evaluated include white blood cell count, platelet, haemoglobin concentration, creatinine, total bilirubin, ALT and AST. Laboratory safety parameters will be graded according to the Division of AIDS (DAIDS) Table for Grading the Severity of Adult and Pediatric Adverse Events, version 2.1 (July 2017). The distribution of Grade 3 and 4 chemistry and haematology laboratory results by time point and treatment group will be presented.

Descriptive statistics including mean, median, standard deviation, maximum, and minimum values and change from baseline by time point, for all and each chemistry and haematology laboratory parameter will be summarized by treatment arm.

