Participants discharged home will not receive further safety assessments. It is not necessary to perform further blood tests on inpatients for the purposes of safety. Routine blood tests taken as part of routine clinical care will be used. If tests are not performed for clinical reasons they will be treated as missing data for analysis.

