⁺Excess biological samples that are being taken for clinical reasons may be stored for future use if no longer required for clinical purposes (Tayside only).

^a For those participants who are intubated.

[∞]These assessments will not be completed if the participant has been discharged from hospital.

^b For the Tayside and Sheffield site only, the day 29 assessments will be carried out face-to-face either at a NHS facility or at the participant's home. Home visits will only be carried out if no one in the household has symptoms of COVID-19.

^cResearch blood samples (Tayside and Sheffield only) and, once discharged, assessments may be completed within +/- 1 day

^dScreening and randomisation may occur on the same day if all eligibility criteria are met. Day of first dose of IMP will be considered as day 1 for the calculation of follow up assessments.

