## Oxygenation

No of days free from oxygen

Duration of new oxygen use

Mechanical ventilation

Number of patients receiving new mechanical ventilation

No of days free from ventilation

Duration of new ventilation used

Duration of hospital stay - days

28-day mortality

Table 10: Safety analyses

	Brensocatib N =	Placebo N =	Effect estimate (95% CI)
% of patients with at least 1 AE			
Incidence of SAEs			
Discontinuation or temporary suspension of treatment			
Changes in white cell count			
Changes in haemoglobin			
Changes in platelets			
Changes in creatinine			
Changes in total bilirubin			
Changes in ALT			
Changes in AST			
Adverse events, n (%):			
Hyperkeratosis (Skin)			
Infections			
Dental complications			

Table 11: Adverse Events

Adverse Event - n (%)	Brensocatib	Placebo
	N =	N =
Death		
Life-threatening		
Required hospitalisation		
Resulted in persistent or significant disability		
Medically significant		
Total		

Table 12: Summary of all adverse events - System Organ Class Level

N = N =	Total	Placebo	Brensocatib
	N=	N =	N =

Number of participants

Number of participants with adverse events

Number of participants without adverse events

Number of adverse events

Cardiac disorders

Eye disorders

Gastrointestinal disorders

General disorders and administration site conditions

Infections and infestations

Injury, poisoning and procedural complications

Investigations

Metabolism and nutrition disorders

Musculoskeletal and connective

tissue disorders

Nervous system disorders

No Code

Psychiatric disorders

Renal and urinary disorders

Respiratory, thoracic and mediastinal disorders

Skin and subcutaneous tissue

disorders

Vascular disorders

Table 13: Summary of all adverse events - Preferred Term Level

Brensocatib	Placebo	Total
N =	N =	N=

Number of participants

Number of participants with adverse

events

Number of participants without adverse

events

Number of adverse events

Abdominal discomfort

Abdominal pain

Acute kidney injury

Arthralgia

Back pain

Blood glucose increased

Bradycardia

Cerebrovascular accident

Chest discomfort

Chest pain

Clostridium difficile infection

Constipation

Cough

Delirium

Diarrhoea

Dizziness

Drug eruption

Dry mouth

Dry skin

Dysarthria

Dyspepsia

Dyspnoea

Dysuria

Electrocardiogram abnormal

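### SAP 10.5 describes clinic laboratory samples that the protocol does not take, and SAP Table 10 attaches effect estimates to laboratory changes seen only in inpatients tested for clinical need

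*SAP*

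**What the plan says.** SAP 10.5 lists laboratory collection at days 0/1, 3, 5, 8 and 11, and at "Day 15 and 29 if able to return to clinic or still hospitalized". It then says that "The distribution of Grade 3 and 4 chemistry and haematology laboratory results by time point and treatment group will be presented", and that descriptive statistics, including change from baseline, "for all and each chemistry and haematology laboratory parameter will be summarized by treatment arm". SAP section 8 bases percentages on the non-missing sample size. SAP 7.4 gives no rule for missing laboratory values.

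The shell headed "Table 10: Safety analyses" in SAP section 16 has an effect-estimate column with 95% confidence interval. Its rows include changes in white cell count, haemoglobin, platelets, creatinine, total bilirubin, ALT and AST. No time point or laboratory model is named. The nearest thing to a method is the line in SAP section 10, "These events will be analysed univariately", and it is not clear that this covers laboratory values.

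The protocol describes a different data source. Its endpoint table (3.7) restricts the laboratory endpoint to hospitalised participants. Section 7.8 records follow-up bloods only where they were already obtained for clinical need. It adds: "Participants discharged home will not receive further safety assessments" and "If tests are not performed for clinical reasons they will be treated as missing data for analysis".

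**The concern.** A reader of SAP 10.5 would believe that the late laboratory tables include outpatients. They cannot. The people with a result on a given day are those still in hospital and also tested for a clinical reason. Both conditions arise after randomisation, and the first is close to what the trial's primary endpoint measures. Comparing one day with another, or one arm with the other, therefore compares differently selected groups.

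This matters more here than in most trials. Protocol 9.2 lists deterioration in renal or liver function and changes in blood count among events not recorded as adverse events, because they are captured as safety endpoints. The laboratory tables are thus the planned home for that signal. An effect estimate and confidence interval in Table 10 would give a selected comparison the look of a randomised one.

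**Working it through.** **1. The collection rules side by side.**

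- SAP 10.5: day 15 and 29 results from participants in hospital or able to attend clinic.
- Protocol 16.4 schedule: full blood count, urea and electrolytes, and liver function tests carry the same footnote mark at every follow-up day: "These assessments will not be completed if the participant has been discharged from hospital". This holds even at day 29, when Tayside and Sheffield see participants face to face; there the research blood sample loses the mark but the three safety rows keep it.
- SAP 5.4, Table 1: repeats the schedule and the footnote. SAP 10.5 therefore contradicts the SAP as well as the protocol.
- Baseline differs: under protocol 7.8, screening bloods are drawn if none were done in the preceding 72 hours. Only follow-up is selected.

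**2. Reproducing the planning figures.** Inputs: the placebo proportions in protocol Table 4 (death 2%, hospital categories 1, 2, 7 and 8%, home 38 and 42%), 1:1 allocation, two-sided 5%, 85% power. Whitehead's formula, N = 12(z₀.₉₇₅ + z₀.₈₅)² / [ln(OR)² (1 − Σp̄ᵢ³)], gives 269.7 at OR 2.0 (stated 272) and 409.5 at OR 1.75 (stated 412). The proportions are being read as intended.

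**3. Upper limit on participants with a late result** (200 per arm).

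- Placebo, alive in hospital: 1 + 2 + 7 + 8 = 18%; 0.18 × 200 = 36.
- Brensocatib, OR 1.75. Death or hospital: odds 0.20/0.80 = 0.25; 0.25/1.75 = 0.1429; probability 0.125. Death: odds 0.02/0.98 = 0.0204; divided by 1.75 = 0.0117; probability 0.0115. Alive in hospital: 0.125 − 0.0115 = 0.1135; × 200 = 22.7, so about 23.
- At OR 2.0 the same steps give 10.1%, about 20.

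Testing for clinical need can only lower these numbers. The documents attach the proportions to day 29 or 28 in the text and to day 15 in a table title, so the limit applies to one late day, not to both.

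**4. Is a trend over time forced?** Assume (the documents give no such risks) one Grade 3–4 risk for the 20% not at home late on and another for the 80% discharged. The rate when all are tested is 0.20 × first + 0.80 × second.

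- 5% and 5%: 5% early, 5% among late inpatients; flat.
- 10% and 2%: 3.6% early, 10% late.
- 10% and 5%: 6% early, 10% late.
- 20% and 5%: 8% early, 20% late.

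The last three assume no recovery. If the late inpatients' own risk falls by more than 64%, 40% and 60% respectively, the observed rate falls instead of rising.

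**5. How large could a between-arm artefact be?** Illustrative model, no drug toxicity: log-logistic discharge with a normal severity factor (coefficient 0.5, 1.0 or 1.5), median stay 8 days (assumed), 80% of controls discharged by day 29 (Table 4), OR 1.75 on discharge, Grade 3–4 probability expit(−2.9 + 0.8 × severity). True prevalence is 6.7% in both arms.

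- Coefficient 1.0: in hospital at days 3, 15 and 29, control 74, 34 and 20%; drug 64, 24 and 13%. Grade 3–4 among inpatients rises from 7.6% to 10.5% (control) and from 8.0% to 11.1% (drug).
- Day 29 at coefficient 0.5: 8.7% v 9.0%. At 1.5: 11.8% v 12.7%.

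The day-29 gap is 0.3 to 0.9 points. With 36 and 23 tested, the standard error of the central difference is √(0.105×0.895/36 + 0.111×0.889/23) = 0.083, or 8.3 points.

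The sign is not fixed either. If instead risk depends only on current hospital category (assumed 30, 20, 10 and 5% from ventilated to no oxygen), the step 3 proportions give 10.0% on placebo and 9.75% on brensocatib.

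**6. Would worst grade per treated participant be free of this?** No. In the same model (coefficient 1.0), mean scheduled in-hospital test days are 2.8 on control and 2.2 on drug. Worst Grade 3–4 over all treated is 18.8% v 15.7% if days are independent given severity, and 5.6% v 5.1% if abnormality persists: a false deficit on drug of about 0.5 to 3 points.

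**The case against.** The strongest reply is that SAP 10.5 only presents and summarises, that protocol 3.7 already limits the endpoint to inpatients, and that SAP section 8 already asks for the non-missing n and for tables annotated with the total population, including missing observations. All of that stands. Much of the reporting requested below is planned; the number alive in hospital by arm and day is not.

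A reader might infer that Grade 3–4 rates must climb with time by construction. The documents do not support that: it needs higher risk in late inpatients with no recovery and no loss of the sickest to death. A reader might also infer a false excess of abnormalities on the drug. The model's gap is under 1 point, far below its standard error, and another plausible assumption reverses the sign. The model is also generous to the concern: it counts the 2% who die as still testable, and it applies the discharge effect from the start although protocol section 2 expects the drug to act over several days.

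The protocol's rule on adverse events is not watertight, since the shell of SAP Table 13 lists acute kidney injury, abnormal liver function tests and raised transaminases. Some such events may reach the adverse-event tables. That softens the stakes without removing them.

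What the reply does not answer is the false collection sentence, or the Table 10 effect estimates with no stated method, time point or population.

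**Conclusion.** The concern holds as an error in the stated data source plus an unsupported between-arm estimate. SAP 10.5 contradicts protocol 3.7, 7.8 and 16.4 and the SAP's own section 5.4. On the planning proportions, at least 80% of placebo and 87.5% of brensocatib participants (OR 1.75) would be at home with no result at the late time point; at most 36 and about 23 of 200 could have one. Those shares follow from the documents' figures and assume 200 per arm, all dosed.

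What follows with certainty is that time points are not comparable with each other and that the arms may not be. Neither the direction of a trend nor that of a between-arm difference follows. The distortion of about 1 point or less rests on an assumed stay, severity link and risk, none of which is in the documents. The case for change is therefore the wrong sentence, the small selected denominators and the apparent precision of Table 10, not a large false drug signal.

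**What to change.** - In SAP 10.5, delete the clause about returning to clinic, and state that all post-baseline results are in-hospital tests ordered for clinical reasons.
- In SAP Table 10, remove the effect estimate and confidence interval from the seven laboratory rows and report those rows descriptively.
- In the laboratory tables, show number tested, number alive in hospital and number treated, by arm and day. The ordinal scale supplies the in-hospital count.
- Optionally, add worst post-baseline grade per treated participant as a shift from baseline grade. It should stand beside the time-point table, not replace it. Label it as observed in hospital and show the number of test days per arm, because earlier discharge lowers the chance of detecting an abnormality.

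This costs SAP wording and some table programming, with no new data. The downside is that the laboratory comparison becomes descriptive only.
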